**Table 3: Schedule of Assessments for PK Study Sub-Cohort:**

Period	SCREENING PERIOD		TREATMENT PERIOD			OBSERVATION PERIOD		
Study Day	Day -21 to Day -1	Day 1		Day 7±2	Day 14±2	Day 28±4	Day 35±2	Day 56±4
	Screening	Day 1 Pre-Dose	Day 1 Dosing	Day 7	Day 14	Day 28	Day 35	Day 56
Additional Exclusion Criteria	√							
24-hour Holter monitor attached						√		
Blood sampling for PK		√		√	√	4 √	√	

### 5.2.3 Nested Phase 1b Safety Sub-Cohort

The first 15 (PK and non-PK) subjects enrolled in the trial will undergo on Day 7 the safety examinations planned for all other subjects plus a physical examination, clinical laboratory tests, and an ECG assessment. Once all 15 subjects in this Nested Phase 1b Safety Sub-Cohort have completed their Day 7 Visit, available blinded safety data (including AEs, LSR scores, clinical laboratory results, and ECG data) from Day 1 through Day 7 will be reviewed within 10 business days by a safety committee consisting of 3 Board-certified physicians not involved in the trial and the Study Medical Monitor. During this blinded interim safety review, enrolled subjects will continue dosing the study drug and study enrollment will remain open.

### 5.2.4 PK Study Sub-Cohort

	DOCUMENT NUMBER: 029-BST-PLN-001	PAGE: 19 of 45
TITLE: Statistical Analysis Plan for study:  A Phase 2 Randomized, Double-Blind, Placebo-Controlled, Parallel-Cohort Study to Evaluate the Efficacy, Safety, Tolerability, and Pharmacokinetics of Once-Daily Application of Topical VDA-1102 Ointment for 28 Days in Subjects with Actinic Keratosis	EFFECTIVE DATE : 22/MAY/2017 REVISION NUMBER : 2.0	

- 5.2.4.1 Of the approximate 84 subjects to be enrolled in this trial, a maximum of 18 subjects (who meet more stringent enrollment criteria than the other subjects enrolled) at select sites, will undergo blood sampling for PK analysis on Day 1 Pre-Dose as well as on Days 7, 14, 28, and 35 . In addition, these subjects will undergo 24-hour cardiac Holter monitoring on Day 28 so that ECGs may be extracted based upon the other safety findings and the plasma PK data.
- 5.2.4.2 Subjects included in this Sub-Cohort may also be included in the Nested Phase 1b Safety Sub-Cohort if they are one of the first 15 subjects to be enrolled into the study.

	DOCUMENT NUMBER: 029-BST-PLN-001	PAGE: 20 of 45
TITLE: Statistical Analysis Plan for study:  A Phase 2 Randomized, Double-Blind, Placebo-Controlled, Parallel-Cohort Study to Evaluate the Efficacy, Safety, Tolerability, and Pharmacokinetics of Once-Daily Application of Topical VDA-1102 Ointment for 28 Days in Subjects with Actinic Keratosis	EFFECTIVE DATE : 22/MAY/2017 REVISION NUMBER : 2.0	

### 5.2.5 Randomization, Blinding and Un-blinding

- 5.2.5.1 Assignment of study drug will be performed using a web-based Interactive Responsive Technology (IRT)-based randomization system (TrialMaster, OmniComm Systems, Fort Lauderdale, FL USA) . On Day 1 Pre-dose Visit, after confirming the subject's eligibility, the Investigator (or his designee) may approve the subject's blinded randomization.
- 5.2.5.2 The web-based IRT will randomize subjects in a fashion that will maintain a balance among the 3 treatment groups (5% and 10% VDA-1102, and placebo) across all subjects enrolled (not per site) and within the PK Study Sub-Cohort. (For further details see "VDA-CP-03 final randomization plan v1.1 15-06-2016.docx")
- 5.2.5.3 Subjects who withdraw or are terminated after the first study dose has been applied will not be replaced in the trial. Subjects who withdraw or are terminated before the first study dose has been applied due to error or violation of an enrollement criterion will be replaced and not included in the Intent-To-Treat (ITT) population.
- 5.2.5.4 All site staff at the investigative sites, Sponsor, CROs, and vendors as well as all enrolled subjects will be masked to the study drug assignments throughout the trial. One pre-designated statistician at MediStat (Tel Aviv, Israel) will have access to the blinded treatment assignments and be responsible for all activities that require un-blinding, including the per protocol Interim Efficacy Analysis.
- 5.2.5.5 In the event of an emergency, the Investigator (or designee) should contact the Study Medical Monitor to discuss the case before un-blinding of an individual subject's treatment code is broken by the site. If the medical condition of the subject warrants immediate un-blinding, the treatment assignment of the subject may be obtained from the IWRS without first consulting the Study Medical Monitor. However, the site must contact the Study Medical Monitor as soon as possible after the un-blinding.

	DOCUMENT NUMBER: 029-BST-PLN-001	PAGE: 21 of 45
TITLE: Statistical Analysis Plan for study: A Phase 2 Randomized, Double-Blind, Placebo-Controlled, Parallel-Cohort Study to Evaluate the Efficacy, Safety, Tolerability, and Pharmacokinetics of Once-Daily Application of Topical VDA-1102 Ointment for 28 Days in Subjects with Actinic Keratosis	EFFECTIVE DATE : 22/MAY/2017 REVISION NUMBER : 2.0	

### 5.3 Selection of Study Population

#### 5.3.1 Study Population

5.3.1.1 In this clinical protocol, study drug will be applied once-daily for 28 days to the Treatment Field on the scalp or face of subjects with AK. Approximately 84 male and female subjects aged 18 or older with 4-8 discrete Grade 1 and/or 2 AK lesions who sign informed consent and meet the study enrollment criteria will be randomly assigned in a double-blinded fashion to 1 of 3 parallel treatment cohorts (5% or 10% VDA-1102 ointment, or placebo) at a ratio of 1:1:1.

#### 5.3.2 Sample Size Justification

5.3.2.1 The primary objective of the trial is to compare the reduction on Day 56 in the number of the AK lesions (or % reduction if baseline measure will be found different between the groups) in the Treatment Field of subjects receiving 5% or 10% VDA-1102 ointment to the reduction in the number of AK lesions in subjects receiving placebo. The sample size calculation was based on demonstrating effect size of 0.83 using a two group t-test with a 0.045 two-sided significance level. The total significance level of 5% was divided between the interim analysis 0.5% (0.005) and the final analysis 4.5% (0.045). The sample size calculation was based on the final significance. The spending function calculation for alpha will be performed using the O'Brien-Fleming approach. Assuming a drop-out rate of 10%, approximately 84 subjects will be recruited in order to complete the study with a sample of approximately 75 evaluable subjects.

5.3.2.2 A sample size of 25 in each group will have 80% power to detect an effect size of 0.83 using a two group T-test with a 0.045 two-sided significance level.

	DOCUMENT NUMBER: 029-BST-PLN-001	PAGE: 22 of 45
TITLE: Statistical Analysis Plan for study: A Phase 2 Randomized, Double-Blind, Placebo-Controlled, Parallel-Cohort Study to Evaluate the Efficacy, Safety, Tolerability, and Pharmacokinetics of Once-Daily Application of Topical VDA-1102 Ointment for 28 Days in Subjects with Actinic Keratosis	EFFECTIVE DATE : 22/MAY/2017 REVISION NUMBER : 2.0	

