### **Statistical Analyses:**

#### ***Efficacy Analysis***

Efficacy analysis will be based on changes from baseline to Day 56 in AK lesions. Comparative analysis of the changes will be applied between each of the active groups versus the placebo group using the two-sample t-test or non-parametric Wilcoxon-Mann-Whitney rank sum test for independent samples or Median test (as is appropriate). In the event that the number of baseline lesions is different between the treatment groups, then relative changes (%) will be analyzed as well.

The overall change and the trend of differences in the changes over time between the groups will be analyzed using mixed-effect model for repeated measures. The model will include changes at any time, the fixed effect time and the interaction of treatment and time. The model will be adjusted for baseline measures and for other relevant covariates.

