#### ***Interim Efficacy Analysis (IEA)***

A single interim efficacy analysis will be conducted as soon as 50% of the subjects have completed their Day 56 Visit. The objective of the IEA is to evaluate the probability of achieving the primary efficacy endpoint at the conclusion of the study. The unblinded data for the interim analysis sub-set will be analyzed by an independent statistician.

The result of the IEA will be a calculated effect size and t-value, which will be based on the difference in the change from baseline in the number of AK lesions for each of the active groups as compared to the placebo group. If baseline measure differs between the groups, then relative change (%) will be tested. The total significance level of 5% was divided between the interim efficacy analysis (0.005) and the final analysis (0.045). The spending function calculation for alpha will be performed using the O'Brien-Fleming methods. In case the distribution of the outcome variable does not approximate normality, the appropriate non-parametric methods will be considered for the interim analysis.

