#### 17.2.1 Efficacy Analysis

The efficacy analysis will be performed with the ITT, mITT, and PP populations (see Section 17.5.2). The primary efficacy endpoint is the change from baseline in number of AK lesions. If the baseline lesions number will be found different between the treatment groups, then relative change (%) will be analyzed as well. The within-group absolute changes (decrease) in AK number of lesions from baseline to each visit will be analyzed using paired t-test or signed rank test for two means (paired observations, as is appropriate).

Comparative analysis of the above changes will be applied between each of the active groups versus the placebo group using the two-sample t-test, the non-parametric Wilcoxon-Mann-Whitney rank sum test for independent samples, or the Median test (as appropriate).

If no statistically significant differences are observed between the two active VDA-1102 groups then these two groups will be pooled and compared to the placebo group in order to achieve higher statistical power.

The overall effect and trend of differences in the changes over time between the groups will be analyzed using a mixed-effect model for repeated measures. The model will include changes from baseline at any time, the fixed effect time, and the interaction of treatment and time. Contrast will be calculated for each time point (Days 7, 14, 28, 35 and 56) versus baseline and the overall effect. The model will be adjusted for baseline measure and for other covariates suspected as affecting the outcome and which will be found different between the treatment groups.

In case the baseline number of lesions differs between the groups, analysis of relative change (%) will be applied as well.

Chi-square test or Fisher's exact test (as is appropriate) will be used for analyzing the difference in percent of subjects with complete clearance of study AK lesions at the end of the treatment. Logistic regression will be applied for analyzing the difference in proportions with adjustment for baseline measure and for other covariates suspected as affecting the outcome and which will be found different between the treatment groups.

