### 17.4 Interim Efficacy Analysis

An interim efficacy analysis will be conducted as soon as approximately 50% of the subjects have completed the study. The objective of the interim analysis is to evaluate the probability to achieve the primary efficacy endpoint.

The data for the interim analysis sub-set will be collected and analyzed for effect size and t-value. Effect size will be calculated based on the difference in the change from baseline in AK lesions for each of the active groups as compared to the placebo group. Relative change (%) will be used if baseline measure will be found different between the groups.

Futility will be based on O'Brien-Fleming boundaries. If the t-value with 22 degrees of freedom is below 0.34, then the study is unlikely to succeed when taken to completion. In case the distribution of the outcome variable will not be found with approximation to normality, then appropriate non-parametric methods will be considered for the interim analysis.

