### 5.1.2 Study Endpoints

#### 5.1.2.1 Primary Efficacy Endpoints:

5.1.2.1.1 Change from baseline in the number of AK lesions within the Treatment Field of each subject on Day 56.

MediStat Statistics in Medicine	DOCUMENT NUMBER: 029-BST-PLN-001	PAGE: 10 of 45
TITLE: Statistical Analysis Plan for study:  A Phase 2 Randomized, Double-Blind, Placebo-Controlled, Parallel-Cohort Study to Evaluate the Efficacy, Safety, Tolerability, and Pharmacokinetics of Once-Daily Application of Topical VDA-1102 Ointment for 28 Days in Subjects with Actinic Keratosis	EFFECTIVE DATE : 22/MAY/2017 REVISION NUMBER : 2.0	

5.1.2.2 Safety Endpoints:

5.1.2.2.1 Assessment of:

- 5.1.2.2.1.1 AEs
- 5.1.2.2.1.2 Vital signs
- 5.1.2.2.1.3 Physical examinations
- 5.1.2.2.1.4 Clinical laboratory parameters
- 5.1.2.2.1.5 Local Skin Reaction (LSR) Scores (individual and total)
- 5.1.2.2.1.6 Electrocardiograms

5.1.2.3 Pharmacokinetic Endpoints:

- 5.1.2.3.1 Assessment of the systemic exposure of VDA-1102 and its primary metabolite jasmonic acid at selected time points during topical application of 5% or 10% VDA-1102 ointment for 28 days in adult subjects with AK

5.1.2.4 Exploratory Endpoints:

- 5.1.2.4.1 The percentage of subjects achieving complete clearance of AK lesions within the Treatment Field on Day 56
- 5.1.2.4.2 Change from baseline in the number of AK lesions within the Treatment Field of each subject on Day 84.

MediStat Statistics in Medicine	DOCUMENT NUMBER: 029-BST-PLN-001	PAGE: 11 of 45
TITLE: Statistical Analysis Plan for study:  A Phase 2 Randomized, Double-Blind, Placebo-Controlled, Parallel-Cohort Study to Evaluate the Efficacy, Safety, Tolerability, and Pharmacokinetics of Once-Daily Application of Topical VDA-1102 Ointment for 28 Days in Subjects with Actinic Keratosis	EFFECTIVE DATE : 22/MAY/2017 REVISION NUMBER : 2.0	

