## 5.6.5 Efficacy Primary Analysis

- 5.6.5.1 The efficacy analysis will be performed with the ITT, mITT and PP populations (see Tables 14.2-1 - 14.2-9). The primary efficacy endpoint is the decrease from baseline in number of AK lesions. The within-group decrease in number of AK lesions from baseline to each visit will be analyzed using paired t-test or signed rank test for two means (paired observations, as is appropriate).
- 5.6.5.2 Comparative analysis of the decrease at Day 56 (mentioned above) will be applied between each of the active groups versus the placebo group using the two-sample t-test, the non-parametric Wilcoxon-Mann-Whitney rank sum test for independent samples, or the Median test (as appropriate) and using the Analysis of Covariance (ANCOVA), after optionally ranking transformation of the variable, with adjustment for sites and for other covariates suspected as affecting the outcome and which will be found different between the treatment groups.
- 5.6.5.3 Figures depicting the number of lesions by visit and by treatment group and depicting the reduction in number of lesions from Baseline to Day 56 will be generated
- 5.6.5.4 Binary variable will be defined based on the decrease in number of AK lesions at Day 56 according to a relevant cutoff (first quartile, median, third quartile or other cutoff computed by ROC curve sensitivity analysis). Comparative analysis of this variable will be applied between each of the active groups versus the placebo group using Chi-square test or Fisher's Exact test and using logistic regression with adjustment for site and for other covariates suspected as affecting the outcome and which will be found different between the treatment groups.

	DOCUMENT NUMBER: 029-BST-PLN-001	PAGE: 31 of 45
TITLE: Statistical Analysis Plan for study:  A Phase 2 Randomized, Double-Blind, Placebo-Controlled, Parallel-Cohort Study to Evaluate the Efficacy, Safety, Tolerability, and Pharmacokinetics of Once-Daily Application of Topical VDA-1102 Ointment for 28 Days in Subjects with Actinic Keratosis	EFFECTIVE DATE : 22/MAY/2017 REVISION NUMBER : 2.0	

5.6.5.5 If the two active VDA-1102 groups trend similarly then these two groups may be pooled and compared to the placebo group in order to achieve higher statistical power.

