## 9. APPENDICES

### APPENDIX I: TABLE SHELLS

Table 14.1-1: Subject Disposition  
 Table 14.1-2: Demographic Data  
 Table 14.1-3: Frequency of Medical History (except Actinic Keratosis) by Category  
 Table 14.1-4: Any Medications within 30 Days Prior to Screening  
 Table 14.1-5: Any Medications between Screening and Day 1 Dosing Visit  
 Table 14.1-6: Disease-related information  
 Table 14.1-7: Dermatological Evaluation at Pre-dose  
 Table 14.1-8: Compliance Data

Table 14.2-1: AK Lesions Count in ITT Population  
 Figure 14.2-1: Total Number of Lesions by Visit and by Study Group in ITT Population  
 Figure 14.2-2: Number of AK Grade  $\geq 2$  lesions by Visit and by Study Group in ITT Population  
 Figure 14.2-3: Adjusted Number of Lesions by Visit and by Study Group in ITT Population

Table 14.2-2: AK Lesions Count in mITT Population  
 Table 14.2-3: AK Lesions Count in PP Population  
 Table 14.2-4: AK Lesions Number: Absolute Changes from Baseline in ITT Population  
 Table 14.2-5: AK Lesions Number: Changes from Baseline in mITT Population  
 Table 14.2-6: AK Lesions Number: Changes from Baseline in PP Population  
 Table 14.2-8: AK Lesions Number: Changes from Baseline for Day 84 Completers

Table 14.2-9: AK Lesions Number: Relative Changes from Baseline in ITT Population (%)  
 Table 14.2-10: AK Lesions Number: Relative Changes from Baseline in mITT Population (%)  
 Table 14.2-11: AK Lesions Number: Relative Changes from Baseline in PP Population (%)  
 Table 14.2-12: AK Lesions Number: Relative Change from Baseline for Day 84 Completers

Table 14.2-13: Frequency of Decrease in AK lesions at Day 56  $\geq$  Cutoff Computed by Sensitivity Analysis/ Relevant Quartile in ITT Population  
 Table 14.2-14: Frequency of Decrease in AK lesions at Day 56  $\geq$  Cutoff Computed by Sensitivity Analysis/ Relevant Quartile in mITT Population  
 Table 14.2-15: Frequency of Decrease in AK lesions at Day 56  $\geq$  Cutoff Computed by Sensitivity Analysis/ Relevant Quartile in PP Population

MediStat Statistics in Medicine	DOCUMENT NUMBER: 029-BST-PLN-001	PAGE: 42 of 45
TITLE: Statistical Analysis Plan for study: A Phase 2 Randomized, Double-Blind, Placebo-Controlled, Parallel-Cohort Study to Evaluate the Efficacy, Safety, Tolerability, and Pharmacokinetics of Once-Daily Application of Topical VDA-1102 Ointment for 28 Days in Subjects with Actinic Keratosis	EFFECTIVE DATE : 22/MAY/2017 REVISION NUMBER : 2.0	

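### The documents contradict each other on whether lesion count or percent reduction is the primary scale when baseline counts differ, and the interim can be run on a scale that the final test does not use

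*SAP*

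**What the plan says.** The SAP defines the primary endpoint as "Change from baseline in the number of AK lesions within the Treatment Field of each subject on Day 56", and Protocol 7.7 and the Synopsis agree. SAP 5.6.5.1 repeats it for the analysis: "The primary efficacy endpoint is the decrease from baseline in number of AK lesions". None of these carries a baseline condition.

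Other sections attach one, in two different ways.

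- **Percent replaces count.** SAP 5.3.2 and Protocol 17.1 give the primary objective as count reduction "or % reduction if baseline measure will be found different between the groups". For the interim, the Synopsis says "If baseline measure differs between the groups, then relative change (%) will be tested" and Protocol 17.4 says "Relative change (%) will be used if baseline measure will be found different between the groups".
- **Percent is added to count.** For the final analysis, Protocol 17.2.1 says that if baseline counts differ "then relative change (%) will be analyzed as well", and later repeats the rule. The Synopsis efficacy text has the same rule: "then relative changes (%) will be analyzed as well".

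The SAP table shells list "AK Lesions Number: Relative Changes from Baseline in ITT Population" and matching tables for the mITT, PP and Day 84 sets, with no condition. Protocol 12.1.3 leaves the interim details to the SAP, which has no section that gives them.

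**The concern.** These rules cannot all be followed. If baselines are judged different, the primary objective calls for percent, the endpoint definition calls for count, and the protocol's final analysis calls for both. The SAP disagrees with itself, because 5.3.2 keeps the switch and 5.6.5.1 omits it.

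The trigger is not defined: there is no test, threshold, set of arms or analysis population. Allocation is randomised 1:1:1, so a baseline difference is chance, and chance would decide which outcome the trial reports. The check can also come out differently in the interim subset and the full set.

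At stake are which quantity the primary test estimates, and whether the interim t-value bears on the test that will be done at the end.

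**Working it through.** **1. The sections side by side**

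| Place | Applies to | Scale if baselines are judged different |
|---|---|---|
| Synopsis endpoints, Protocol 7.7, SAP 5.1.2.1, SAP 5.6.5.1 | Primary endpoint and analysis | Count, no condition |
| Protocol 17.1, SAP 5.3.2 | Primary objective | Percent instead of count |
| Synopsis interim text, Protocol 17.4 | Interim | Percent instead of count |
| Synopsis efficacy text, Protocol 17.2.1 | Final | Count, with percent added |
| SAP Appendix I | Tables | Both, no condition |

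**2. The plan's own design figure**

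Inputs from SAP 5.3.2: effect size 0.83, 25 per group, two-sided alpha 0.045, 10% drop-out. Noncentral t with df = 2×25 − 2 = 48 and noncentrality 0.83 × √(25/2) = 2.93 gives power of 80.7% (stated: 80%). Recruitment is 75/(1 − 0.10) = 83.3, so 84, as stated. The design reproduces. The 0.83 is standardised and tied to neither scale, so fixing one scale does not change the sample size.

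**3. Size of the problem, by simulation**

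The documents give no clearance rate or baseline distribution, so these are assumptions:

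- 40,000 trials, 25 per arm, with the first 12 per arm as the interim (2×12 − 2 = 22, the degrees of freedom in Protocol 17.4).
- Baseline counts 4–8 (the eligibility range), either equally likely or weighted 0.40, 0.25, 0.15, 0.10, 0.10.
- Beta-binomial clearance with beta parameters summing to 3, mean 25% on placebo, and 25% (inert) or 48% (effective) on active. The effective case has a standardised effect of 0.73–0.80.

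*How often the trigger fires.* Read as a three-arm ANOVA at p<0.05, 0.10 or 0.20, it fires in about 5%, 10% or 20% of trials. If any numeric difference counts, it fires in over 99%.

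*Interim and final on different scales.* If the final is always on count (SAP 5.6.5.1), this equals the interim trigger rate: about 5%, 10% or 20%. If percent replaces count at both looks, it is about 7%, 13% or 22%, because the two checks can disagree.

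*Type I error, one dose against placebo, nominal 4.5%.* Count alone gives 4.4% and percent alone 4.4–4.6%. A mechanical switch on the two arms' baseline p-value gives 4.2–4.3%. Claiming success on either scale, with both available in every trial, gives 5.7–5.8%. Including further runs that assumed 30% clearance and counting error of SD 0.5–1.0, the ranges are about 4.2–4.5% for the switch and 5.6–6.1% for either scale.

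*Disagreement on significance, effective drug.* It is 9.8–10.7% over all trials, and 19.9–20.6% where the two arms' baselines differ at p<0.05. As a share of all trials that is about 0.05 × 0.20 = 1%.

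*Interim call at t = 0.34.* When the p<0.05 trigger fires, the two scales fall on opposite sides in 14.0–17.3% of inert-drug trials and 6.0–7.4% of effective-drug trials. Trigger and differing call together:

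- Inert: 0.050 × 0.140 = 0.70% and 0.049 × 0.173 = 0.85%.
- Effective: 0.051 × 0.060 = 0.31% and 0.049 × 0.074 = 0.36%.

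At a p<0.20 trigger these joint figures rise to about 2.4–2.9% (inert) and 1.3% (effective).

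**The case against.** The sponsor can answer that the endpoint is fixed. Every formal endpoint statement names the count, SAP 5.6.5.1 has no switch, and SAP 5.6.1.2 gives the SAP precedence on analysis. On that view the parenthesis in SAP 5.3.2 is carried over from Protocol 17.1. Much of this stands for the final analysis, and it would be wrong to say that the plan has no defined primary endpoint. But 5.6.1.2 also says that differences from the protocol are stated, and this one is not. The parenthesis is in the SAP itself. Nothing in the SAP replaces the interim rule.

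A reader might infer that the additive wording creates two primary p-values. The documents do not support that: Protocol 17.2.1 names the count as primary and does not call the percent analysis primary. The SAP shells show both scales whatever the baseline check finds.

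A reader might also infer that the switch inflates type I error to nearly 6%, or that about 8–10% of inert-drug interims would get a different futility call. Both figures need the percent scale to be in play in every trial. With percent available only when ANOVA p<0.05, even claiming success on either scale gives 4.4–4.6%.

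Finally, the switch responds to something real. When baselines differ at p<0.05, the unadjusted count test rejects in 6.0–6.3% of null trials, against about 4.4% for percent. That is a reason to adjust for baseline count. It does not require changing the outcome. Protocol 17.4 also describes a low interim t only as a sign of unlikely success and does not mandate stopping.

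**Conclusion.** The contradiction is in the text and does not depend on any simulation. The documents give three incompatible instructions for the scale when baselines differ, with an undefined trigger, and the only interim instruction can put the interim t-value on a scale that the final test does not use.

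The numerical effect is small under a conventional trigger. At p<0.05 it fires in about 5% of trials; where it fires and the drug works, the scales disagree on significance in about 20%. A changed futility call because of the switch occurs in about 0.7–0.9% of inert-drug and 0.3–0.4% of effective-drug trials. It becomes material if the trigger is loose or judged by eye, or if both scales are kept available and the better one is claimed. All these figures rest on assumed baseline and clearance distributions.

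This should be corrected because it concerns the primary outcome and can be settled by wording.

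**What to change.** - Delete the percent-reduction alternative from SAP 5.3.2, Protocol 17.1, Protocol 17.4 and the Synopsis interim text.
- In the Synopsis efficacy text and both places in Protocol 17.2.1, replace the conditional rule with a statement that percent change is always reported, as supportive only.
- State once, in the SAP, that absolute change in lesion count is the only primary scale at both interim and final.
- Name baseline lesion count as a prespecified covariate in the SAP 5.6.5.2 ANCOVA and the 5.6.5.6 repeated-measures model. Both now adjust for site and for covariates that turn out to differ between groups, which is the same undefined trigger. The protocol's repeated-measures model did name the baseline measure.

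The cost is SAP wording and a short protocol clarification. The sample size stays at 25 per group and 84 in total, and Tables 14.2-9 to 14.2-12 remain as supportive output.
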